3.2 Exclusion Criteria

- 3.2.1 Patients who have had chemotherapy within 2 weeks prior to entering the study
- 3.2.2 All toxicities attributed to prior anti-cancer therapy other than alopecia must have resolved to grade 1 or baseline
- 3.2.3 Patients may not be receiving any other investigational agents.
- 3.2.4 Patients with known brain metastases or cranial epidural disease unless accurately treated with radiotherapy and/or surgery (including radiosurgery) and stable for at least 4 weeks before first dose of study treatment. These individuals should be excluded from this clinical trial because of their poor prognosis and because they often develop progressive neurologic dysfunction that would confound the evaluation of neurologic and other adverse events. Eligible subjects must be neurologically asymptomatic and without corticosteroid treatment at the time of the first dose of study treatment.
- 3.2.5 History of allergic reactions attributed to compounds of similar chemical or biologic composition to pembrolizumab, cabozantinib_or other agents used in study. Patients with documented previous immune related toxicities which led to discontinuation of a checkpoint inhibitor.
- 3.2.6 Concomitant anticoagulation with oral anticoagulants (eg, warfarin), direct thrombin inhibitors (e.g., dabigatran), direct factor Xa inhibitors betrixaban, or platelet inhibitors (eg, clopidogrel).

 Allowed anticoagulants are the following:
 - a. Prophylactic use of low-dose aspirin for cardio-protection (per local applicable guidelines) and low-dose low molecular weight heparins (LMWH).
 - b. Therapeutic doses of LMWH or anticoagulation with direct factor Xa inhibitors rivaroxaban, edoxaban, or apixaban in subjects without known brain metastases who are on a stable dose of the anticoagulant for at least 1 week before first dose of study treatment without clinically significant hemorrhagic complications from the anticoagulation regimen or the tumor.
- 3.2.7 The subject has prothrombin time (PT)/INR or partial thromboplastin time (PTT) test ≥ 1.3 x the laboratory ULN within 7 days before the first dose of study treatment.
- 3.2.8 Uncontrolled intercurrent illness including, but not limited to, the following conditions:
 - a. ongoing or active infection
 - b. symptomatic congestive heart failure
 - uncontrolled hypertension defined as sustained blood pressure (BP) > 150 mm Hg systolic or > 100 mm Hg diastolic despite optimal antihypertensive treatment
 - d. Stroke (including transient ischemic attack [TIA]), myocardial infarction (MI), or other ischemic event, or thromboembolic event (eg, deep venous thrombosis, pulmonary embolism) within 6 months before first dose
 - e. unstable angina pectoris
 - f. cardiac arrhythmia

- g. evidence of tumor invading GI tract, active peptic ulcer disease, inflammatory inflammatory bowel disease (eg, Crohn's disease), diverticulitis, cholecystitis, symptomatic cholangitis or appendicitis, acute pancreatitis, acute obstruction of the pancreatic duct or common bile duct, or gastric outlet obstruction.
- h. Abdominal fistula, GI perforation, bowel obstruction, or intra-abdominal abscess within 6 months before first dose.
 Note: Complete healing of an intra-abdominal abscess must be confirmed before first dose.
- i. Clinically significant hematuria, hematemesis, or hemoptysis of > 0.5 teaspoon (2.5 ml) of red blood, or other history of significant bleeding (eg, pulmonary hemorrhage) within 12 weeks before first dose.
- j. Cavitating pulmonary lesion(s) or known endotracheal or endobronchial disease manifestation.
- k. Lesions invading any major blood vessels.
- I. Other clinically significant disorders that would preclude safe study participation:
 - i. Serious non-healing wound/ulcer/bone fracture
 - ii. Uncompensated/symptomatic hypothyroidism
 - iii. Moderate to severe hepatic impairment (Child-Pugh B or C)
- m. psychiatric illness/social situations that would limit compliance with study requirements.
- 3.2.9 Major surgery (e.g., laparoscopic nephrectomy, GI surgery, removal or biopsy of brain metastasis) within 2 weeks before first dose of study treatment. Minor surgeries within 10 days before first dose. Subjects must have complete wound healing from major surgery or minor surgery before first dose of study treatment. Subjects with clinically relevant ongoing complications from prior surgery are not eligible.
- 3.2.10 Prior treatment with cabozantinib
- 3.2.11 Corrected QT interval calculated by the Fridericia formula (QTcF) > 500 ms per electrocardiogram (ECG) within 28 days before first dose of study treatment.

Corrected QT (QTc) = QT / ³√RR

QT: duration of QT interval RR: duration of RR interval

Note: If a single ECG shows a QTcF with an absolute value > 500 ms, two additional ECGs at intervals of approximately 3 min must be performed within 30 min after the initial ECG, and the average of these three consecutive results for QTcF will be used to determine eligibility.

- 3.2.12 Receipt of any type of small molecule kinase inhibitor (including investigational kinase inhibitor) within 2 weeks before first dose of study treatment.
- 3.2.13 History of another primary cancer within the last 3 years with the exception of non-melanoma skin cancer, early-stage prostate cancer, or curatively treated cervical carcinoma in-situ and not treated with systemic therapy.
- 3.2.14 Inability to comply with study and follow-up procedures as judged by the Investigator

- 3.2.15 Patients must not be pregnant or nursing due to the potential for congenital abnormalities and the potential of this regimen to harm nursing infants.
- 3.2.16 Has squamous cell or undifferentiated gastric cancer.
- 3.2.17 Has received prior cytotoxic, biologic or other systemic anticancer therapy including investigational agents within 2 weeks prior to randomization.
- 3.2.18 Radiation therapy for bone metastasis within 2 weeks, any other radiation therapy within 4 weeks before first dose of study treatment. Systemic treatment with radionuclides within 6 weeks before the first dose of study treatment. Subjects with clinically relevant ongoing complications from prior radiation therapy are not eligible.
- 3.2.19 Has received a live vaccine within 30 days prior to the first dose of study intervention. Examples of live vaccines include, but are not limited to, the following: measles, mumps, rubella, varicella/zoster (chicken pox), yellow fever, rabies, Bacillus Calmette–Guérin (BCG), and typhoid vaccine. Seasonal influenza vaccines for injection are generally killed virus vaccines and are allowed; however, intranasal influenza vaccines (eg, FluMist®) are live attenuated vaccines and are not allowed.
- 3.2.20 Has a diagnosis of immunodeficiency or is receiving chronic systemic steroid therapy (in dosing exceeding 10 mg daily of prednisone equivalent) or any other form of immunosuppressive therapy within 7 days prior to the first dose of study intervention.
- 3.2.21 Has severe hypersensitivity (Grade ≥ 3) to pembrolizumab or cabozantinib and/or any of their excipients.
- 3.2.22 Has an active autoimmune disease that has required systemic treatment in past 2 years (i.e., with use of disease-modifying agents, corticosteroids or immunosuppressive drugs). Replacement therapy (e.g., thyroxine, insulin, or physiologic corticosteroid replacement therapy for adrenal or pituitary insufficiency) is not considered a form of systemic treatment and is allowed.
- 3.2.23 Has a history of (non-infectious) pneumonitis that required steroids or has current pneumonitis.
- 3.2.24 Has an active infection requiring systemic therapy.
- 3.2.25 Has a known history of human immunodeficiency virus (HIV) infection.

 Note: No HIV testing is required unless mandated by local health authority.
- 3.2.26 Has a known history of active tuberculosis (TB; Bacillus tuberculosis).
- 3.2.27 Has a history or current evidence of any condition (eg, known deficiency of the enzyme dihydropyrimidine dehydrogenase), therapy, or laboratory abnormality that might confound the results of the study, interfere with the participant's participation for the full duration of the study, or is not in the best interest of the participant to participate, in the opinion of the treating investigator.

3.3 **Inclusion of Women, Minorities, Vulnerable Populations** Both men and women and members of all races and ethnic groups are eligible for this trial. Non-English speaking, deaf, hard of hearing and illiterate individuals are eligible for this trial.

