 - Low dose low molecular weight heparins (LMWH) for prophylactic use are allowed if clinically indicated and the benefit outweighs the risk per the Investigator's discretion.
 - Therapeutic doses of LMWH or the direct factor Xa oral inhibitors rivaroxaban, edoxaban, or apixaban are allowed if clinically indicated (e.g., for the treatment of DVT), and the benefit outweighs the risk per the Investigator's discretion. See section 7.1.2 for management of thromboembolic complications while on study. See section 4.1.2.2 for prohibited anticoagulants. Accepted clinical guidelines regarding appropriate management while receiving any kind of anticoagulation therapy must be followed. This includes, but is not limited to, subject education regarding the potential adverse drug reactions, monitoring laboratory parameters, dose adjustments (e.g., due to kidney dysfunction). Caution is warranted in settings associated with an increased risk for bleeding such as gastrointestinal cancers, urothelial cancers, gastrointestinal mucosal abnormality (e.g., mucositis), renal or hepatic impairment, thrombocytopenia, arterial hypertension, or prior history of gastrointestinal bleed. For direct factor Xa inhibitors, the potential for drug-drug interaction with other concomitant medications, as well as gastrointestinal absorption, should be considered. Aspirin and other nonsteroidal anti-inflammatory drugs (NSAIDs) should not be used concomitantly with heparin or factor Xa inhibitors due to the increased risk for bleeding complications. The risks and benefits of the use of anticoagulants should be reassessed on a regular basis. For more information regarding the use of anticoagulants, refer to the prescribing information of the anticoagulant and accepted clinical practice guidelines.

4.1.2.2 Prohibited or Restricted Therapy:

The following therapies are prohibited until study treatment has been permanently discontinued:

- Any investigational agent or investigational medical device.
- Oral anticoagulation with coumarin agents (e.g., warfarin), direct thrombin inhibitors (e.g., dabigatran), direct factor Xa inhibitor betrixaban, platelet inhibitors (e.g., clopidogrel), and chronic use of aspirin above low dose levels for cardio-protection per local applicable guidelines), until 4 weeks after cabozantinib has been permanently discontinued.

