Hemorrhagic events, including serious and sometimes fatal events, have been reported with cabozantinib. Subjects should be monitored for bleeding events with serial complete blood counts and physical examination while on study. The risk of hemorrhage in cabozantinib-treated subjects with brain metastases has not been thoroughly analyzed. Subjects enrolled with treated and stable brain metastases should be monitored with a high index of suspicion if symptoms that could be due to a CNS hemorrhage occur.

Cabozantinib should be discontinued in subjects with serious and life-threatening bleeding events or recent hemoptysis (≥ 2.5 mL of red blood).

Thromboembolic events

Refer to section 7.1.2

Hypertension

Table 10 provides treatment guidelines for hypertension deemed related to cabozantinib. Blood pressure should be monitored in a constant position visit to visit, either sitting or supine in a relaxed setting. Decisions to reduce or interrupt the dose of study treatment must be based on BP readings taken by a medical professional and must be confirmed with a second measurement at least 5 minutes following the first measurement.

Cabozantinib should be discontinued in subjects with hypertensive emergency.

Table 10: Management of Hypertension Associated with Cabozantinib

Criteria for Dose Modifications	Treatment/Cabozantinib Dose Modification				
Subjects NOT receiving optimized anti-hypertensive therapy					
> 150 mm Hg (systolic) ^a and < 160 mm Hg OR > 100 mm Hg (diastolic) and < 110 mm Hg	 Optimize antihypertensive medications by adding new or additional antihypertensive medications and/or increase dose of existing medications. Reduce cabozantinib treatment by one dose level if optimal antihypertensive therapy (usually to include 3 agents) does not result in BP <150 mm Hg systolic or <100 mm Hg diastolic If subject is symptomatic interrupt cabozantinib treatment 				

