7.1.1 Contraindications

Cabozantinib and pembrolizumab have no known contraindications.

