7.1.2 Special Warnings and Precautions for Use *Cabozantinib*

Dermatologic toxicity: Palmar-plantar erythrodysesthesia syndrome (PPES) was commonly observed in clinical trials; severe PPES (≥ grade 3) also occurred. May require treatment interruption, dosage reduction, and/or discontinuation.

GI toxicity: Diarrhea was commonly observed in cabozantinib-treated patients in clinical trials. May require therapy interruption and/or dosage reduction. Cabozantinib is associated with a moderate emetic potential; antiemetics are recommended to prevent nausea/vomiting. [US Boxed Warning]: Cometriq: Serious GI perforations and fistulas have been reported when used for medullary thyroid cancer; discontinue for GI perforation or fistula formation. May be fatal. Tracheal/esophageal fistulas were also noted; some cases were fatal. GI fistula/perforation (including fatal perforations) were also reported in patients treated with cabozantinib. Monitor for signs/symptoms of perforations and fistulas, including abscess and sepsis. May require therapy discontinuation.

Hemorrhage: [US Boxed Warning]: Cometriq: Serious and occasionally fatal hemorrhage (including hemoptysis and gastrointestinal) has occurred with cabozantinib when used for medullary thyroid cancer. Monitor for signs/symptoms of bleeding and do not administer to patients with severe hemorrhage or a recent history of hemorrhage or hemoptysis. Severe hemorrhage has also been reported in patients with renal cell cancer and hepatocellular carcinoma, including grade 3 or higher events. Do not administer to patients who have a recent history of hemorrhage, including hemoptysis, hematemesis, or melena. Discontinue for grade 3 or 4 hemorrhagic events.

Hypertension: Treatment emergent hypertension was commonly seen in clinical trials (including grade 3 or higher toxicity and hypertensive crisis). Do not initiate cabozantinib in patients with uncontrolled hypertension. Monitor blood pressure prior to therapy initiation and regularly thereafter; withhold for hypertension that is

uncontrolled with appropriate medical management. May require cabozantinib dosage reduction and/or therapy discontinuation.

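### The bleeding history that bars entry (3.2.8 i) is narrower than the one that bars cabozantinib dosing (7.1.2), and the sections need reconciling

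*Combined protocol and SAP*

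**What the plan says.** Four places in the protocol bear on bleeding before the first dose.

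- **Eligibility, 3.2.8 i.** Entry is barred for "Clinically significant hematuria, hematemesis, or hemoptysis of > 0.5 teaspoon (2.5 ml) of red blood, or other history of significant bleeding". The criterion closes with one example and a time window: "eg, pulmonary hemorrhage) within 12 weeks before first dose". Melena is not named.
- **Warnings, 7.1.2, cabozantinib hemorrhage paragraph.** This contains two instructions. The boxed-warning sentence says "do not administer to patients with severe hemorrhage or a recent history of hemorrhage or hemoptysis". A later sentence says "Do not administer to patients who have a recent history of hemorrhage, including hemoptysis, hematemesis, or melena". Neither gives a volume, a grade, a test of clinical significance or a time window.
- **Contraindications, 7.1.1.** Immediately before that text the protocol states: "Cabozantinib and pembrolizumab have no known contraindications".
- **Anticoagulants, 4.1.2.1.** Gastrointestinal cancers are listed among settings of raised bleeding risk, and the same list ends with "thrombocytopenia, arterial hypertension, or prior history of gastrointestinal bleed". These are reasons for caution, not bars.

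No eligibility criterion refers to 7.1.2, and the 7.1.2 hemorrhage paragraph does not refer to 3.2.8 i.

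**The concern.** Section 3 decides who is enrolled, and 7.1.2 says who should not be given one of the two study drugs. If the second group is wider than the first on bleeding history, some patients are eligible for a regimen that the same protocol says not to give them. Bleeding from the stomach shows itself as hematemesis or melena, so in a gastric and gastroesophageal trial this is a history that screening staff can expect to meet.

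The stake is patient safety and consistent conduct. A site working from the eligibility list alone could dose a patient against the protocol's own warning. Two sites, or two investigators, could treat the same history differently and both point to protocol text in support.

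**Working it through.** No formula applies, because the point depends on no effect size, sample size or error rate. The check is to set 3.2.8 i beside 7.1.2 and take each kind of bleeding history in turn.

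One ambiguity comes first. In 3.2.8 i the volume limit of more than 2.5 mL may attach to hemoptysis alone or to all three named bleeding types. The table takes both readings. Rows 1 to 5 concern bleeding within 12 weeks before first dose that also counts as *recent* under 7.1.2.

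| History | 3.2.8 i, volume limit on hemoptysis only | 3.2.8 i, volume limit on all three | 7.1.2 |
|---|---|---|---|
| 1. Hematemesis not judged clinically significant | Not excluded | Not excluded | Do not give |
| 2. Hematemesis judged clinically significant, 2.5 mL or less | Excluded | Excluded only if it counts as other significant bleeding | Do not give |
| 3. Hemoptysis of 2.5 mL or less, not otherwise judged significant bleeding | Not excluded | Not excluded | Do not give |
| 4. Melena not judged significant | Not excluded | Not excluded | Do not give |
| 5. Melena judged significant | Excluded by the catch-all | Excluded by the catch-all | Do not give |
| 6. Any bleeding more than 12 weeks before first dose | Not excluded | Not excluded | Unclear: *recent* is undefined |

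Rows 1, 3 and 4 show the mismatch under either reading. Row 2 depends on the reading. Row 5 shows no mismatch. Row 6 is an open question, not a demonstrated conflict.

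Next, does other text close rows 1, 3 and 4?

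- The opening of 3.2.8 makes its list non-exhaustive, so an investigator may exclude for an unlisted condition. It does not oblige exclusion.
- Exclusion 3.2.27 lets the treating investigator exclude a patient whose participation is not in that patient's interest. It is discretionary, and mentions neither bleeding nor 7.1.2.
- Section 7.1.1 does not help. Its statement that there are no contraindications sits badly with an instruction, in the next section, not to give the drug to a described group.
- The 4.1.2.1 text governs anticoagulant use and settles nothing about eligibility.

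None of these makes the entry rule as wide as the dosing instruction.

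**The case against.** The strongest reply is that 7.1.2 is not a trial rule. It is headed as warnings and precautions, repeats labelling for another cabozantinib product in medullary thyroid cancer, and even tells the reader to withhold axitinib, which is not a study drug. Section 4.4 has its own hemorrhage paragraph and does not send the reader to 7.1.2 for that topic. On this view 3.2.8 i is the operative criterion and its 12 weeks supplies the meaning of *recent*.

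Part of this stands. The time window is not shown to conflict, and some of 7.1.2 plainly cannot bind. But the bleeding sentences are worded as instructions. Section 4.4 refers to 7.1.2 for thromboembolism, wound healing, osteonecrosis and infections, so the section is in operational use, and 10.6 requires the study to be run as the protocol describes. A site is not told which parts of 7.1.2 bind.

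A reader might also draw stronger conclusions that the documents do not support:

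- *That sites cannot obey both passages.* They can, by not enrolling the patient. No text compels enrolment or dosing.
- *That melena as such is admitted.* Only melena not judged significant gets through.
- *That all hematemesis of 2.5 mL or less is admitted.* That holds only if the volume limit reaches hematemesis, which the wording leaves open.
- *That 4.4 contradicts 3.2.8 i.* Section 4.4 stops cabozantinib for "recent hemoptysis (≥ 2.5 mL of red blood", whereas entry excludes more than 2.5 mL. One is an on-treatment rule and the other an entry rule, and they differ only at exactly 2.5 mL.
- *That the number of patients affected can be estimated.* The 3% gastrointestinal hemorrhage and 5% grade 3 or higher hemorrhage in 7.1.4 are adverse-reaction rates on cabozantinib. They say nothing about bleeding before entry.
- *That patients will be registered, left undosed and lost from the evaluable set.* Evaluability does require cycle 1 day 1 treatment (6.1.1), and patients are not replaced (4.9). But medical history and eligibility are reviewed at screening, so a bleeding history would normally surface before registration.

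**Conclusion.** The inconsistency is real but limited. A patient with recent hematemesis or melena not judged clinically significant, or with small-volume hemoptysis, meets the section 3 criteria on bleeding and also falls under an instruction not to receive cabozantinib. Discretion permits exclusion but does not require it. This rests on two assumptions: that the bleeding sentences in 7.1.2 are meant as instructions for this trial, as they are worded, and that the bleeding is recent in whatever sense the sponsor intends.

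The size in patients cannot be given from the documents. There is no effect on the statistical design: the 19 and 27 evaluable patients, the limits of 2 and 4 progression-free patients, and the error rates do not depend on how the bleeding rule is worded. The point deserves correction because it concerns safety at first dose in a population whose tumour site the protocol itself associates with bleeding.

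**What to change.** Reconcile 3.2.8 i, 7.1.1 and the hemorrhage paragraph of 7.1.2 so that a single bleeding-history rule governs both eligibility and first dose, and cross-refer the sections. The reconciled text should make clear which bleeding it covers, whether any significance or volume limit applies and to which types, and what period counts as recent. What each of these should be is a clinical decision for the sponsor.

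The cost is a wording change at the next amendment and a line on the eligibility checklist. A few borderline patients may change eligibility status as a result. No statistical section needs to change.

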4.0 TREATMENT PLAN

4.1 Treatment Dosage and Administration

4.1.1 Patients will be treated with cabozantinib 40 mg p.o. on days 1-21 and pembrolizumab 200 mg i.v. on day 1 every 21 days.

REGIMEN DESCRIPTION					
Agent	Premedications; Precautions	Dose	Route	Schedule	Cycle Length
Cabozantinib	None	40 mg daily	At least 1 hour before or at least 2 hours after eating	Days 1-21	3 weeks
Pembrolizumab	Supportive care for infusion reactions per institutional guidelines	200 mg in 50 cc NS 0.9% over 30 min	IV	Day 1	days)

4.1.2 Concomitant Medications

4.1.2.1 Allowed Therapy:

- Antiemetics and antidiarrheal medications are allowed prophylactically according to standard clinical practice if clinically indicated.
- Granulocyte colony-stimulating factors (G-CSF or GM-CSF) are allowed if used per clinical guidelines (e.g., ASCO or ESMO guidelines).
- Bisphosphonates or RANK-L inhibitors can be used to control bone loss or hypocalcemia if the benefit outweighs the risk per the Investigator's discretion. Note: osteonecrosis of the jaw has been reported in subjects using bisphosphonates (Section 7.1.2). Oral examinations are recommended at screening to determine eligibility and periodically during the study. In addition, subjects should be advised regarding oral hygiene practice and to quickly report symptoms to the Investigator. Frequent monitoring for potentially overlapping toxicities with study treatment is recommended. Withhold cabozantinib for at least 3 weeks prior to scheduled dental surgery or invasive dental procedures, if possible. Withhold cabozantinib for development of ONJ until complete resolution
- Transfusions and hormone replacement should be utilized as indicated by standard clinical practice.
- Inhaled, intranasal, intra-articular, and topical corticosteroids are allowed if minimal systemic absorption. Systemic corticosteroids are allowed for control of infusion reactions or irAEs and must be tapered to a dose level ≤ 10 mg/day of prednisone equivalent before next administration of the IO agent. Prophylactic steroid treatment for subjects with contrast allergies prior to tumor imaging is allowed.

- Individualized anticoagulation therapy with heparin or direct factor Xa inhibitors rivaroxaban, edoxaban, or apixaban is allowed if it can be provided safely and effectively under the following circumstances:
 - At the time of first dose of study treatment:
 - Low dose low molecular weight heparins (LMWH) for prophylactic use are allowed if clinically indicated and the benefit outweighs the risk per the Investigator's discretion.
 - Therapeutic doses of LMWH or the direct factor Xa inhibitors rivaroxaban, edoxaban, or apixaban are allowed if the subject has no evidence of brain metastasis, has been on a stable dose of the anticoagulant for at least 1 week, and has had no clinically significant hemorrhagic complications from the anticoagulation regimen or the tumor. See Section 4.1.2.2 for prohibited anticoagulants.
 - · After first dose of study treatment:
 - Low dose low molecular weight heparins (LMWH) for prophylactic use are allowed if clinically indicated and the benefit outweighs the risk per the Investigator's discretion.
 - Therapeutic doses of LMWH or the direct factor Xa oral inhibitors rivaroxaban, edoxaban, or apixaban are allowed if clinically indicated (e.g., for the treatment of DVT), and the benefit outweighs the risk per the Investigator's discretion. See section 7.1.2 for management of thromboembolic complications while on study. See section 4.1.2.2 for prohibited anticoagulants. Accepted clinical guidelines regarding appropriate management while receiving any kind of anticoagulation therapy must be followed. This includes, but is not limited to, subject education regarding the potential adverse drug reactions, monitoring laboratory parameters, dose adjustments (e.g., due to kidney dysfunction). Caution is warranted in settings associated with an increased risk for bleeding such as gastrointestinal cancers, urothelial cancers, gastrointestinal mucosal abnormality (e.g., mucositis), renal or hepatic impairment, thrombocytopenia, arterial hypertension, or prior history of gastrointestinal bleed. For direct factor Xa inhibitors, the potential for drug-drug interaction with other concomitant medications, as well as gastrointestinal absorption, should be considered. Aspirin and other nonsteroidal anti-inflammatory drugs (NSAIDs) should not be used concomitantly with heparin or factor Xa inhibitors due to the increased risk for bleeding complications. The risks and benefits of the use of anticoagulants should be reassessed on a regular basis. For more information regarding the use of anticoagulants, refer to the prescribing information of the anticoagulant and accepted clinical practice guidelines.

4.1.2.2 Prohibited or Restricted Therapy:

The following therapies are prohibited until study treatment has been permanently discontinued:

- Any investigational agent or investigational medical device.
- Oral anticoagulation with coumarin agents (e.g., warfarin), direct thrombin inhibitors (e.g., dabigatran), direct factor Xa inhibitor betrixaban, platelet inhibitors (e.g., clopidogrel), and chronic use of aspirin above low dose levels for cardio-protection per local applicable guidelines), until 4 weeks after cabozantinib has been permanently discontinued.
- Any non-protocol systemic anticancer treatment (e.g., chemotherapy, immunotherapy, radionuclides, drugs or herbal products used specifically for the treatment of the cancer under investigation).

- Immunosuppressive agents including immunosuppressive doses of systemic corticosteroids with exceptions as stated in Section 4.1.2.1.
- Live vaccines are prohibited while on study and until 5 months after last dose of IO
 agent (e.g., intranasal influenza, measles, mumps, rubella, oral polio, BCG, yellow
 fever, varicella, and TY21a typhoid vaccines). The use of inactivated (killed)
 vaccines for the prevention of infectious disease is permitted.
- Metamizole (dipyrone) because of its potential for causing agranulocytosis.

The following therapies should be avoided until study treatment has been permanently discontinued or until otherwise specified:

- Local anticancer treatment including palliative radiation, ablation, embolization, or surgery with impact on tumor lesions should not be performed until radiographic progression per RECIST 1.1 has been established.
- Erythropoietic stimulating agents (e.g., epoetin alfa and darbepoetin alfa) should not be used based on a report of increased risk of tumor recurrence/progression associated with erythropoietin (Wright et al 2007).
- Concomitant medications that are known to prolong the QTc interval should be avoided in subjects who receive cabozantinib until they have permanently discontinued cabozantinib treatment (refer to http://www.qtdrugs.org for a list of drugs which have the potential to prolong the QTc interval).
- Chronic co-administration of cabozantinib with strong inducers of the CYP3A4 family (e.g., phenytoin, carbamazepine, rifampin, rifabutin, rifapentine, phenobarbital, and St. John's Wort) may significantly decrease cabozantinib concentrations and should be avoided. Selection of alternate concomitant medications with no or minimal CYP3A4 enzyme induction potential is recommended.
- Caution must be used when discontinuing treatment with a strong CYP3A4 inducer in a subject who has been concurrently receiving a stable dose of cabozantinib, as this could significantly increase the exposure to cabozantinib.
- Co-administration of cabozantinib with strong inhibitors of the CYP3A4 family (e.g., boceprevir, conivaptan, posaconazole, ketoconazole, itraconazole, clarithromycin, atazanavir, indinavir, nefazodone, nelfinavir, saquinavir, ritonavir, lopinavir, telaprevir, telithromycin, and voriconazole) may increase cabozantinib concentrations and should be avoided. Grapefruit, star fruit, and Seville oranges may also increase plasma concentrations of cabozantinib and should be avoided.

